5.9.1.2. To Continue Treatment within a Cycle- Schedule B (modified weekly)

Amendment 10 Update: Following completion of the Schedule B Dose Escalation portion of the study, the CRC reviewed safety, PK and efficacy data from both dosing schedules and based this review, made the decision to discontinue further investigation of Schedule B dosing. While patients currently receiving IMGN853 study treatment according to Schedule B will continue to do so, new patients enrolled to the study will receive treatment according to Schedule A only.

In the absence of otherwise dose-limiting toxicity, for a patient to continue treatment within a cycle, the following criteria must be met.

- ANC must be $\geq 1.0 \times 10^9 / L (1,000 / \mu L)$
- Platelet count must be $\ge 75 \times 10^9 / L (75,000 / \mu L)$
- All non-hematologic toxicities for which a causal association to study treatment cannot be ruled out, must be ≤ Grade 2 (except alopecia) or returned to baseline; the exception to this rule is treatment-emergent eye disorders, which must have recovered to ≤ Grade 1 or baseline
- A minimum of 7 days (~168 hours) must have elapsed between IMGN853 doses

If the patient does not meet these criteria, dosing will be delayed and the patient should be reevaluated within 72 hours. Dosing may resume if these criteria have been met. If the criteria are not met due to insufficient recovery from a treatment-related toxicity, then that week's dose will be considered "missed".

The use of granulocyte growth factors in accordance with ASCO guidelines may be implemented at the discretion of the treating physician after Cycle 1.

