4.1.3.2. Schedule B

Schedule B dose escalation is complete and the MTD is 2 mg/kg (AIBW). The modified weekly schedule will not be evaluated further in this study. In Schedule B, the starting dose of IMGN853 will be 1.1 mg/kg, which is 1/3 the 3.3 mg/kg Q3W dose level, which was deemed clinically safe in nine patients.

Patients will be enrolled in cohorts of 3 to 6 patients until the MTD is defined (Section 4.1.3.3). Planned dose levels are listed below in Table 4 and will be administered based on AIBW body weight. Based on emerging data, the CRC will decide the magnitude of the dose escalation and may determine that exploration of lower or intermediate dose levels is warranted. If at any time, the administration of IMGN853 on a weekly basis is deemed to be suboptimal or PK/ Pharmacodynamics data supports a less frequent dosing regimen, the decision may be made by the CRC to select the less frequent dosing schedule.

A patient will be deemed non-evaluable for dose escalation decisions and will not be counted toward the total cohort size if the patient did not receive a full course of treatment (i.e., all planned doses of IMGN853 for the first treatment cycle) and did not experience a DLT; or discontinued from the study prior to completing necessary safety evaluations through the end of the first cycle of treatment and did not experience a DLT. Non-evaluable patients will be replaced unless accrual to the cohort has stopped due to the occurrence of at least two patients with DLT.

ImmunoGen, Inc. Confidential Page 58 of 138

Dose Level	Dose (mg/kg)	Percent Increase From Previous Dose Level	Number of Patients (Planned)
1	1.1	N/A	3 or 4-6
2	1.8	65%	3 or 4-6
3	2.5	40%	3 or 4-6
4	3.3	32%	3 or 4-6

Table 4: Planned Dose Levels (Schedule B; Dosed by AIBW)

NOTE: If additional dose exploration is required to define the MTD then dose escalation may proceed at increments $\leq 25\%$. The CRC will determine the magnitude of the dose escalation increments following review of available clinical and PK data from patients treated in the current cohort.

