4.1.4. Definition of Dose-Limiting Toxicity (DLT)

Dose limiting toxicity (DLT) will be defined as a TEAE or abnormal laboratory value related to study treatment (i.e., assessed as unrelated to disease, intercurrent illness, or concomitant medications), including those TEAEs and abnormal laboratory values that result in a failure to

ImmunoGen, Inc. Confidential Page 59 of 138

meet the criteria for re-treatment. DLTs will be considered related to the investigational agent unless there is clear evidence of an alternative explanation and this attribution is agreed to by the CRC.

For the purposes of dose escalation and determination of the MTD, only DLTs that occur during the first cycle will be necessarily considered for decisions regarding dose escalation. Clinically significant toxicities or treatment-emergent adverse events that meet the definition of dose limiting but occurring after Cycle 1 (dose modifying events) may be considered when determining the RP2D.

If a patient experiences a DLT as outlined in Table 5, the study treatment must be stopped and the toxicity (ies) in question must be followed until resolution or stabilization. If treatment is to be resumed then retreatment criteria must be met (Section 5.9.3) and administration must be resumed at a lower dose (Section 4.1.3).

Table 5: DLT Definitions

TOXICITY	DLT DEFINITION CRITERIA			
Dose delays	Failure to meet re-treatment criteria within the specified timeframe			
Hematology	CTCAE Grade 4 neutropenia ≥ 7 days.			
	• CTCAE Grade 3 or 4 neutropenia with single temperature reading ≥ 38.3°C or sustained temperature reading of > 38°C for > 1 hour			
	CTCAE Grade 3 thrombocytopenia, associated with clinically- significant bleeding that requires transfusion therapy			
	CTCAE Grade 4 thrombocytopenia			
Non-hematologic and other DLTs	• ≥ CTCAE Grade 3 nausea or vomiting despite the use of optimal anti- emetic treatments			
	• ≥ CTCAE Grade 3 diarrhea despite the use of optimal anti-diarrheal treatments			
	• Other non-hematologic toxicities of CTCAE ≥ Grade 3 except for the following:			
	AEs related to underlying disease			
	o Alopecia			
	 CTCAE Grade 3 fatigue 			
	 Lymphopenia is not considered DLT unless accompanied by clinically-significant infection 			
	 Isolated, asymptomatic Grade 3 abnormalities in biochemistry laboratory values that last for ≤ 7 days. This includes electrolyte abnormalities that respond to medical intervention. 			

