5.7.1.2. Modified Weekly Schedule (Days 1, 8 and 15, Every 28 Days)

For logistical reasons such as holidays, Day 1 delays in the scheduled study treatment for up to 3 days is permitted. Additionally, shifts in the start of a new cycle by -1 or up to +3 days will be permitted in Cycles \geq 3. If patients do not meet retreatment criteria on Days 8 and 15 of a given cycle, the dose should be omitted. A delay of 1 day in the dosing of Days 8 and 15 is permitted; if a delay occurs, subsequent dosings on that cycle should be shifted by 1 day. Intervals <7 days between dosings are not permitted. The start of the next cycle should remain the same.

ImmunoGen, Inc. Confidential Page 64 of 138

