5.9. Treatment Guidelines

5.9.1. Re-treatment Criteria

5.9.1.1. To Begin a New Cycle of Treatment

In the absence of otherwise dose-limiting toxicity, for a patient to begin a new cycle of therapy, the following criteria must be met.

- ANC must be $\geq 1.5 \times 10^9 / L (1,500 / \mu L)$
- Platelet count must be $\geq 75 \times 10^9/L (75,000/\mu L)$
- All non-hematologic toxicities for which a causal association to study treatment cannot be ruled out, must be ≤ Grade 2 (except alopecia) or returned to baseline; the exception to this rule is treatment-emergent ocular symptoms, which must have recovered to < Grade 1 or baseline

If the patient does not meet these criteria, dosing will be delayed and the patient should be reevaluated within 48-72 hours. Dosing may resume if these criteria have been met. However, if the next cycle is delayed by greater than 14 days because of insufficient recovery from a treatment-related toxicity, this will be viewed as a dose-limiting event (Section 4.1.4). For patients treated on either dosing schedule, if the next cycle is delayed due to treatment-related toxicity by greater than 21 days then the patient should be removed from study treatment. In such cases, continuation of study treatment may be considered for those patients who have experienced clinical benefit if agreed upon between the Sponsor and the Investigator.

The use of granulocyte growth factors in accordance with ASCO guidelines may be implemented at the discretion of the treating physician after Cycle 1.

ImmunoGen, Inc. Confidential Page 74 of 138

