6.3. Dose Limiting Toxicities (DLTs)

DLTs will be defined as a TEAE or abnormal laboratory value related to study treatment (i.e., assessed as unrelated to disease, intercurrent illness, or concomitant medications), including those TEAEs and abnormal laboratory values that result in a failure to meet the criteria for retreatment. DLTs will be considered related to the study treatment unless there is clear evidence of an alternative explanation and this attribution is agreed to by the CRC.

For the purposes of dose escalation and determination of the MTD, only DLTs that occur during the first cycle will be necessarily considered for decisions regarding dose escalation. Clinically significant toxicities or treatment-emergent adverse events that meet the definition of dose limiting but occurring after Cycle 1 (dose modifying events) may be considered when determining the RP2D.

A listing of DLTs will be provided.

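### A Schedule B Cycle 1 dose withheld for drug toxicity has no single DLT or evaluability status, so the Schedule B DLT rate, and any MTD based on it, depends on which passage is followed

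*Protocol*

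**What the plan says.** **DLT definition.** Protocol 4.1.4 and SAP 6.3 define a DLT as a treatment-related event or laboratory abnormality, "including those TEAEs and abnormal laboratory values that result in a failure to meet the criteria for retreatment". Protocol Table 5 adds a dose-delay row: "Failure to meet re-treatment criteria within the specified timeframe". For escalation, "only DLTs that occur during the first cycle will be necessarily considered for decisions regarding dose escalation".

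**New-cycle rule.** Protocol 5.9.1.1 classes a long delay as dose-limiting and cross-refers to 4.1.4; its sentence begins "if the next cycle is delayed by greater than 14 days because of insufficient recovery from a treatment-related toxicity, this will be viewed as".

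**Within-cycle rule, Schedule B.** Protocol 5.7.1.2 says: "If patients do not meet retreatment criteria on Days 8 and 15 of a given cycle, the dose should be omitted". Protocol 5.9.1.2, which sits under the heading Re-treatment Criteria, asks for re-evaluation within 72 hours and then says: "If the criteria are not met due to insufficient recovery from a treatment-related toxicity, then that week's dose will be considered" missed. It does not refer to 4.1.4.

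**Evaluability.** Protocol 4.1.3.2 makes a Schedule B patient non-evaluable, not counted and replaced under this condition: "did not receive a full course of treatment (i.e., all planned doses of IMGN853 for the first treatment cycle) and did not experience a DLT". There is no exception for a dose withheld because of the drug. Protocol 5.10.1, headed for patients withdrawn before the end of Cycle 1, says that those whose Cycle 1 is incomplete because of an adverse event are not replaced.

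**Analysis.** SAP Table 5 assigns the DLT analysis to the Safety population, which is everyone who received a dose. SAP 6.3 plans a DLT listing only.

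**Result.** The protocol (synopsis, 4.1.1, 4.1.3.2) gives the Schedule B MTD as 2.0 mg/kg. SAP 1.1 says that Schedule B evaluation stopped before an MTD was identified.

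**The concern.** MTD is a primary endpoint, and protocol section 2 applies the objectives to both schedules. One Cycle 1 event can enter the Schedule B DLT rate in three ways: as a DLT, as a reason to remove and replace the patient, or as a non-DLT in a patient who stays in the denominator. The documents contain support for each.

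The events at issue fail the Day 8/15 criteria but meet no other row of protocol Table 5. Examples are a Grade 2 eye disorder (5.9.1.2 requires Grade 1 or baseline, while Table 5 starts at Grade 3 for non-hematologic events), Grade 3 fatigue (exempted in Table 5), and Grade 3 neutropenia without fever. Ocular toxicity matters most, because section 1.10.2 gives limiting it as a main reason for exploring the modified weekly schedule.

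If such patients were dropped and replaced, the DLT proportion would describe only patients who could receive all three Cycle 1 doses or who had another DLT. A reader of the planned DLT listing could not tell whether this happened.

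**Working it through.** **Step 1: is the event a DLT?**

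| Source | Status of a toxicity-withheld Day 8/15 dose |
|---|---|
| Protocol 4.1.4 general sentence; SAP 6.3 | Can be read as a DLT: it results in failure of re-treatment criteria |
| Protocol Table 5, dose-delay row | Open: depends on a timeframe not defined within a cycle |
| Protocol 5.7.1.2 | Dose omitted; DLT status not mentioned |
| Protocol 5.9.1.2 | Missed; no link to 4.1.4 |

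Candidate timeframes are more than 14 days (5.9.1.1, new cycle), 72 hours (5.9.1.2) and a 1-day delay (5.7.1.2). Table 5 does not say which applies.

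**Step 2: if it is not a DLT, is the patient counted?** Protocol 4.1.3.2: no, and replaced. Protocol 5.10.1: not replaced, although it does not clearly cover a patient who misses one dose and stays on treatment. SAP Table 5: included, because all dosed patients are.

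**Step 3: size.** The plan states no operating characteristics for the 3+3 rule, so there is no figure to reproduce. The documents give no event rates, so the following is an illustration.

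Inputs: *d*, the assumed proportion with an unequivocal protocol Table 5 DLT; *m*, the assumed proportion who miss a Cycle 1 dose through toxicity and have no other DLT. The rule is protocol 4.1.3.3: a level is cleared with 0 DLTs in 3, or with 1 in 3 followed by 0 in the next 3.

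P(cleared) = (1−p)³ + 3p(1−p)² × (1−p)³

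Take *d* = 0.15 and *m* = 0.20:

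- Counted as DLT: p = 0.15 + 0.20 = 0.35. P = 0.2746 + 0.4436 × 0.2746 = **0.396**.
- Replaced: p = 0.15/(1 − 0.20) = 0.1875. P = 0.5364 + 0.3713 × 0.5364 = **0.736** (simulation: 0.735). About 6 × 0.20/0.80 = 1.5 patients are replaced per 6 evaluable.
- Kept as non-DLT: p = 0.15. P = 0.6141 + 0.3251 × 0.6141 = **0.814**.

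Starting with 4 patients, the first two become 0.341 and 0.701.

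| *d* | *m* | Counted as DLT | Replaced | Kept as non-DLT |
|---|---|---|---|---|
| 0.10 | 0.05 | 0.814 | 0.897 | 0.906 |
| 0.15 | 0.05 | 0.709 | 0.798 | 0.814 |
| 0.20 | 0.05 | 0.600 | 0.686 | 0.709 |
| 0.25 | 0.05 | 0.494 | 0.572 | 0.600 |
| 0.10 | 0.10 | 0.709 | 0.887 | 0.906 |
| 0.10 | 0.20 | 0.494 | 0.862 | 0.906 |
| 0.15 | 0.20 | 0.396 | 0.736 | 0.814 |
| 0.20 | 0.20 | 0.309 | 0.600 | 0.709 |

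With *m* = 0.05, the gap between counting and replacing is 0.08 to 0.09 (0.572 − 0.494 = 0.078; 0.798 − 0.709 = 0.089). The gap between counting and keeping is 0.09 to 0.11.

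**Step 4: one dose level.** Suppose 6 evaluable patients have 1 DLT: 1/6 = 16.7%, which meets the MTD definition. If one further patient had been replaced after a toxicity-missed dose, counting that patient as a DLT gives 2/7 = 28.6%. With two, it is 3/8 = 37.5%, above the 33% limit. Kept as non-DLTs, the same patients give 1/7 = 14.3% and 1/8 = 12.5%.

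**The case against.** The strongest reply is that the plan can be read coherently. The only delay expressly tied to 4.1.4 is the new-cycle delay of more than 14 days, and 5.9.1.2 applies only when there is no other dose-limiting toxicity. On that reading one omitted weekly dose is not a DLT. This stands as a possible reading. It is not the only one, because the general sentence in 4.1.4 and SAP 6.3 carries no time limit and the Day 8/15 criteria are re-treatment criteria by heading and by name.

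A reader might infer that replacement by itself favours accepting a dose. It does so only against counting the event as a DLT. If the event is not a DLT, replacement shrinks the denominator, raises the apparent rate from 15% to 18.75%, and lowers clearance from 0.814 to 0.736.

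The affected group is also narrow. Grade 4 thrombocytopenia, and Grade 4 neutropenia lasting 7 days or more, are DLTs without bleeding or fever. The Cohort Review Committee sees all safety data (4.1.2) and can expand a level, halt escalation or explore lower levels. The SAP keeps all dosed patients in the Safety population and plans dose counts, drug-administration listings and tables of events leading to dose delay. These points limit the practical effect, but none gives the event one status or yields a Schedule B DLT proportion with a stated denominator.

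**Conclusion.** The conflict is real and touches a primary endpoint. For Schedule B, the DLT numerator and denominator both depend on which passage is followed. At the assumed 15% and 20%, the probability of clearing a level is 0.40, 0.74 or 0.81 across the three readings. At 5% missed doses the first two differ by less than 0.10. These figures rest on assumed rates, independent patients and mechanical use of the 3+3 rule.

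A reader might infer that 2.0 mg/kg was set too high. The documents do not support that: they do not report how many Schedule B patients missed a Cycle 1 dose through toxicity or were replaced, and SAP 1.1 says that no Schedule B MTD was identified. Nor do they settle that the event is a DLT. Which rule is clinically right is not judged here. Schedule B is closed to new patients and the RP2D comes from Schedule A, so the RP2D is unaffected.

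**What to change.** Reconcile protocol 4.1.4 and its Table 5, 5.9.1.2, 4.1.3.2 and 5.10.1 with SAP 6.3 and SAP Table 5, so that a Cycle 1 Day 8 or 15 dose withheld for treatment-related toxicity has one DLT status and one evaluability status. Reconcile SAP 1.1 with the protocol on whether a Schedule B MTD exists.

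In SAP 6.3, add a table by Schedule B dose level with the number treated, the number replaced, the number with a toxicity-missed Cycle 1 dose, and the DLT proportion under each reading: counted as DLT, excluded as non-evaluable, and kept as non-DLT. State in the study report whether the Schedule B MTD conclusion depends on the reading. This adds no new rule for declaring an MTD.

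The cost is wording and one small table from data already collected. The downside is that the stated Schedule B MTD may need a qualification.

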5.9.2. Follow-up for DLTs and AEs Leading to Discontinuation

Patients who experience a non-laboratory DLT must be evaluated weekly, at a minimum, until resolution to \leq Grade 1 or baseline and then at least monthly until return to baseline or stabilization of the event, whichever comes first. For abnormal laboratory values that qualify as a DLT, patients will be followed twice weekly until values return to \leq Grade 1 or baseline, whichever comes first.

Patients who discontinue the study for AE or an abnormal laboratory value must be followed at least once a week for 4 weeks, and subsequently at 4-week intervals until resolution or stabilization of the adverse event or laboratory abnormality, whichever occurs first.

5.9.3. Criteria for Re-Initiation of Study Treatment Following Occurrence of a DLT

Study treatment will be stopped if a patient experiences a DLT at any time during the study. It may resume, with applicable dose adjustments (Section 5.9.4.1) if the following criteria are met:

- ANC must be $\ge 1.5 \times 10^9 / L (1500 / \mu L)$
- Platelet count must be $\geq 75 \times 10^9/L (75,000/\mu L)$
- All clinically-significant non-hematologic toxicities for which a causal association to study treatment cannot be ruled out must be ≤ Grade 1 (except alopecia) or returned to baseline

ImmunoGen, Inc. Confidential Page 75 of 138

If the patient does not meet these criteria, dosing will be delayed and the patient should be reevaluated within 48-72 hours. Dosing may resume if these criteria have been met. However, if the next cycle is delayed by greater than 14 days because of insufficient recovery from a treatment-related toxicity, this may be viewed as a dose-limiting event (Section 4.1.4). For patients treated on either schedule, if the next cycle is delayed due to treatment-related toxicity by greater than 21 days then the patient should be removed from study treatment. In such cases, continuation of study treatment may be considered for those patients who have experienced clinical benefit if agreed upon between the Sponsor and the Investigator.

5.9.4. Dose Modification Guidelines

5.9.4.1. Dose Reduction Following DLT

Patients who develop DLTs or adverse events requiring holding of the study drug may resume treatment at a reduced dose level as shown in Table 11 provided the criteria outlined in Section 5.9.4.2 are met.

Table 11: Dose Modification Guidelines

Dosing Schedule	If the patient was receiving IMGN853 at:	Dose should be reduced to:	
Schedule A	6.0 mg/kg	5.0 mg/kg	
	5.0 mg/kg	4.0 mg/kg	
Schedule B*	2.0 mg/kg	1.8 mg/kg	
	1.8 mg/kg	1.1 mg/kg	

^{*}IMGN853 should be dose-reduced one dose level; a second dose reduction may be allowed as needed. Dose reductions to intermediate dose levels may be allowed based on emerging data with the approval of the Sponsor.

Amendment 10 Update: Schedule B will not be evaluated further in the current study.

5.9.4.2. Criteria for Re-initiation of Study Treatment Following Occurrence of a DLT

The AE reverts to baseline or \leq Grade 1 within 14 days of the next scheduled Day 1 dose; the patient is clearly deriving clinical benefit, and the patient has an otherwise favorable risk/benefit profile.

Once a dose level reduction has occurred, patients must remain at this reduced dose.

5.9.5. Discontinuation of Study Treatment Due to Toxicity

Study treatment should not be resumed in the case of the following treatment-related events.

- ≥ Grade 3 cardiac event
- other non-hematologic events of Grade 4 severity
- Failure to meet re-treatment criteria within 21 days due to insufficient recovery from a treatment-related toxicity. In such cases, continuation of study treatment may be considered for those patients who have experienced clinical benefit if agreed upon between the Sponsor and the Investigator.

ImmunoGen, Inc. Confidential Page 76 of 138

5.10. Removal of the Patients from the Trial or Study Drug

The patient or legal guardian acting on behalf of the patient is free to withdraw consent and discontinue participation in the study at any time without prejudice to further treatment. For this protocol, patients withdrawn for reasons other than toxicity during Cycle 1 may be replaced.

Patients will be removed from the study when their disease worsens, and show no clinical benefit. Additionally, a patient's participation in the study may be discontinued at any time at the discretion of the Investigator. The following may be justifiable reasons for the Investigator to remove a patient from the study:

- The patient suffers an intolerable adverse event
- Non-compliance, including failure to appear at one or more study visits
- The patient was erroneously included in the study
- The study is terminated by the Sponsor

If a patient or the patient's legal guardian(s), acting on behalf of the patient, discontinues participation in the study, or the patient is discontinued by the Investigator, the reason for discontinuation must be captured in the eCRF. Any AEs experienced up to the point of discontinuation must be documented on the AE eCRF. All SAEs, and those AEs assessed by the Investigator as at least possibly related to study drug should continue to be followed until they resolve or stabilize, whichever comes first.

5.10.1. Replacement of Patients who are Withdrawn Prior to the End of Cycle 1

Only patients who sign the informed consent and receive any study treatment will be considered enrolled. If an enrolled patient is discontinued from study treatment for reasons other than safety (e.g., withdrawal of consent, non-compliance, death due to disease progression) prior to the end of Cycle 1, he or she will be replaced (i.e., an additional patient will be added to the cohort). Patients who do not complete Cycle 1 due to an AE will not be replaced. Patients who are replaced will not be considered in making dose-escalation decisions, but if possible, will be followed for safety and other assessments according to the protocol.

